The outcome of this study will be the dichotomized responses at follow-up to specific items obtained from the DNWQ. The DNWQ is used to examine how primary school children perceive their psychosocial well-being and learning environment in school. The DNWQ has been a mandatory assignment for the public schools in Denmark and was introduced in 2015. DNWQ consist of 20 items for children in 0th to 3rd grade assessed using a three-point Likert scale ranging from 1 to 3. For children in 4th to 9th grade the DNWQ consist of 40 items assessed on a five-point Likert scale ranging from 1 to 5.

For this study we have selected 7 items to best describe the psychosocial well-being in our cohort. We will include completed questionnaires at time of inclusion and at follow-up. At follow-up, we will prioritize completed questionnaires closest to two years from time of inclusion visit.

All answers will be dichotomized into: Good well-being / Poor well-being, depending on the item. Responses 1 and 2 for grades 0-3 and response 1-3 for grades 4-9 will be characterized as poor well-being.

The psychosocial well-being items:

Question 1:

Are you happy with your school? (0th to 9th grade)

Question 2:

Do you feel lonely at school? (0th to 3rd grade)

Do you feel lonely? (4th to 9th grade)

Question 3:

Is anyone teasing you so that you feel sad? (0th to 3rd grade)

Have you been bullied this school year? (4th to 9th grade)

Question 4:

Does your stomach ache when you are at school? (0th to 3rd grade)

How often does your stomach ache? (4th to 9th grade)

Question 5:

Are you good at solving your problems? (0th to 3rd grade)

How often can you find a solution to problems, just by trying hard enough? (4th to 9th grade)

Question 6:

Can you concentrate during class? (0th to 9th grade)

Question 7:

Are you good at helping each other in class? (0th to 3rd grade)

Most students in my class are friendly and helpful. (4th to 9th grade)

Data sources and study variables

Data sources

TM-Sund: TM-Sund is a data capturing tool used by community health nurses and has been used to record data on height and weight obtained from health check-ups at the school and data on children attending or deciding not to participate in the intervention.

The National Registers at Statistic Denmark (DST): DST will be used to identify relevant co-variables such as proxies for Socioeconomic status, immigration background, family structure and psychiatric diagnoses of the child or parents.

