The Department of IT and Learning (STIL): The DNWQ will be obtained from STIL, Ministry of Children and Youth.

Study variables:

We wish to include the following co-variates at inclusion:

- BMI z-score (e.g. 3.0 SD) (19)
- Sex (girl/boy)
- Highest completed Household Education (HHE)
 - “Short”: Primary school (UNESCO’s International Standard Classification of Education (ISCED) level 1-2).
 - “Middle”: Highschool, vocational education, and similar shorter education (ISCED level 3-5).
 - “Long”: Tertiary education at bachelor level or higher (ISCED level 6-8)
- Immigration status (Danish origin / immigrants 1. or 2. generation)
- Disposition for mental illness (lifetime) (yes / no)
- Mental illness, child (lifetime) (yes / no)
- Family structure (two caretakers / not-two caretakers)

Statistical methods:

All statistical analyses will be performed using Stata/SE 15 (StataCorp LP, College Station, Texas, USA). All statistical tests will be two-sided with a significance level at 0.05.

For the characteristics at inclusion

- Normally distributed data will be analyzed using a one-way ANOVA (several means) and a t-test (two means).
- Non-normally distributed data will be analyzed using a Wilcoxon ranksum test (2 groups) and Kruskal-Wallis test (> 2 groups).
- Categorical variables will be analyzed using a Fisher's exact test.

For missing data (education, immigration status, and family-type), a multiple imputation (MI) with chained equations will be utilized to replace missing values with imputed values. Rubin's rule will be applied to obtain overall estimates of 100 imputed datasets.

We will perform the analyses in several steps:

Firstly, the McNemar's test will be used to investigate potential change in psychosocial well-being from time of inclusion to follow-up for each of the dichotomized items (Q1-Q7) in all three groups. All items will be dichotomized into: Good well-being/Poor well-being.

Secondly, the impact in psychosocial well-being for children declining participation will be compared to the intervention group and to the non-intervention group by a logistic regression. The logistic regression analysis will be reported as both a crude (only including the outcome and the groups) and a multivariable model. The psychosocial well-being at inclusion will act as an explanatory variable in the models.

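### Well-being at inclusion appears to enter the models only as good/poor. Using the original answer is a cheap improvement, and the plan should settle whether the crude model contains it.

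*Combined protocol and SAP*

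**What the plan says.** The Outcome section sets the endpoint: "The outcome of this study will be the dichotomized responses at follow-up to specific items obtained from the DNWQ". It applies the split generally, "All answers will be dichotomized into: Good well-being / Poor well-being, depending on the item", with these cut-points: "Responses 1 and 2 for grades 0-3 and response 1-3 for grades 4-9 will be characterized as poor well-being". Grades 0-3 answer on a form "assessed using a three-point Likert scale ranging from 1 to 3"; grades 4-9 use a five-point form. Statistical methods repeats the split when introducing the McNemar tests: "All items will be dichotomized into: Good well-being/Poor well-being".

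For the group comparisons, Statistical methods specifies logistic regression reported as "a crude (only including the outcome and the groups) and a multivariable model". The next sentence reads "The psychosocial well-being at inclusion will act as an explanatory variable in the models". Tables 3 and 4 label the two rows for each item *univariable* and *multivariable*.

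Well-being at inclusion is not among the co-variates under Study variables, nor in the prioritized list of seven. The plan does not say whether it counts against the limit of one co-variate per 10 observations of the least common outcome, and it does not name the model to be interpreted.

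**The concern.** Families declined, attended or were never invited, so the groups may differ in well-being at the start. The same item at inclusion is the most direct control for that difference.

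If the term is coded good/poor, answers 1 and 2 on the 3-point form become identical. On the 5-point form, answers 1, 2 and 3 become identical, and so do 4 and 5. Any group difference inside those classes stays in the group odds ratio, although the finer answers are in the data from which the split is made.

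The two sentences about the models also pull apart. A model with only the outcome and the groups has no baseline term, yet the next sentence puts one in the models without restriction. Two analysts could fill the first row of Tables 3 and 4 differently.

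**Working it through.** **No figure to reproduce.** The plan gives no sample size, event count, baseline rate or expected group difference. From the documents come the two response scales, the cut-points, the binary follow-up outcome and the model type. Everything else below is an assumption.

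**Set-up.** Let G = 1 for decliners, with no effect of declining.
- Latent well-being at inclusion: W0 = Z - d·G. At follow-up: W1 = r·W0 + sqrt(1 - r²)·e. Z and e are standard normal.
- Answers are cut from these scores, with or without added item error, and the plan's poor categories are applied.
- A logistic model for poor well-being at follow-up is fitted with G and (a) no baseline term, (b) good/poor baseline, (c) all baseline categories.

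The true odds ratio (OR) is 1.00, so any other value is bias. Share of leftover bias removed = 1 - ln(OR under c) / ln(OR under b).

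**With item error** (d = 0.2-0.4 SD, r = 0.5-0.7, item reliability 0.7). The rows give the lower and upper ends of the ranges.

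| Form | OR, good/poor | OR, original categories | Share of leftover removed |
|---|---|---|---|
| 3-point, low | 1.08 | 1.07 | 1 - 0.0677/0.0770 = 12% |
| 3-point, high | 1.24 | 1.21 | 1 - 0.1906/0.2151 = 11% |
| 5-point, low | 1.09 | 1.06 | 1 - 0.0583/0.0862 = 32% |
| 5-point, high | 1.25 | 1.17 | 1 - 0.1570/0.2231 = 30% |

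With other assumed answer distributions the shares were roughly 11-15% (3-point) and 30-35% (5-point). With no baseline term the 5-point OR was about 1.14-1.47, so good/poor adjustment already does much of the work. A linear score did about as well as separate category indicators.

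**Without item error** (d = 0.2 or 0.5 SD, r = 0.3-0.7, 20% or 40% poor).
- Good/poor baseline removed 56-67% of the crude log OR.
- The full 3-point answer removed 61-77%.
- The full 5-point answer removed 85-97%.
- Adjusting for the latent score itself gave 0.98-1.02, which confirms that the set-up has no true effect.
- Example (d = 0.5, r = 0.5, 20% poor): on the 3-point form 1.54 crude, 1.20 good/poor, 1.16 full; on the 5-point form 1.56, 1.22 and 1.07.

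The gain on the 5-point form therefore depends heavily on assumed item reliability. On the 3-point form it is modest either way.

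**Degrees of freedom.** One good/poor term uses 1. A linear score within each form plus a form indicator uses 2 slopes + 1 = 3, which is 2 more. Full indicators across both forms give 3 + 5 = 8 cells, or 7 degrees of freedom, which is 6 more.

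**The case against.** The good/poor coding is inferred. The sentence introducing the covariate does not state it. This stands, but no other coding is offered, and a plan that meant the original scale would still need to say so.

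A reader might infer that the first row of Tables 3 and 4 certainly omits baseline well-being and is therefore defective. The documents support neither step. The parenthesis and the *univariable* label point to omission; the following sentence points the other way, unless the models there means only the multivariable ones. An unadjusted row beside an adjusted one is ordinary reporting, it compares the declared follow-up outcome, and within-group change is tested separately by McNemar.

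A reader might also infer that residual bias would favour finding harm from declining. Nothing in the plan says that decliners start with worse well-being. The Objective is neutral and the tests are two-sided ("All statistical tests will be two-sided with a significance level at 0.05"). Families might equally decline because the child is doing well, which would reverse the bias.

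The strongest objection concerns size. Children are 5 to 10 years old at inclusion. If school starts at about age 6 (an assumption), most inclusion answers are on the 3-point form, where the OR moves by only 0.01-0.03. On that form good is a single answer, so no recoding can separate children within it. With reliability 0.7, most of the leftover bias remains after the change on either form. The simulations also omit the seven listed co-variates, which may absorb part of the imbalance. All of this stands, and it limits the point to a cheap improvement.

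**Conclusion.** The point holds as a low-cost improvement plus one contradiction to resolve. On the natural reading, the plan coarsens its baseline adjustment without need and leaves more residual imbalance between self-selected groups than the held data require. If the groups differ at inclusion by 0.2-0.4 SD, with correlation 0.5-0.7 and reliability 0.7, the original answers remove roughly 11-15% of the leftover log OR bias on the 3-point form and about 30-35% on the 5-point form. Measurement error and coarse items account for the remainder. The actual imbalance, its direction and the mix of forms cannot be determined from the documents, so no bias of a given size or sign can be attributed to this study. The conflict over the content of the crude model rests on the wording alone and needs no assumptions.

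**What to change.** Change the wording in Statistical methods and the row labels in Tables 3 and 4:

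- Keep the dichotomized follow-up outcome.
- Keep a first row with outcome and groups only, labelled as unadjusted, and limit the baseline sentence to the adjusted models.
- In every adjusted model, include the inclusion answer to the same item on its original scale, as a linear score within the form answered at inclusion plus a form indicator. The forms differ in scale and partly in wording, so raw scores should not be pooled across them.
- State that these terms are always retained and are not ranked against the seven listed co-variates.
- Name the adjusted estimate as the one to be interpreted.

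The data are already held. The cost is about 2 more degrees of freedom per model than one good/poor term, or 6 more with full indicators. By the plan's own one-per-10 yardstick, 2 degrees of freedom correspond to 2 × 10 = 20 observations of the least common outcome. Exempting the terms from the limit therefore loosens the guard against overfitting for items with few events, and that should be acknowledged where event counts are low.

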The multivariable model will be adjusted for no more than 1 co-variate per 10 observations of the least common outcome. The co-variates are listed in prioritized order: 1) BMI z-score 2) sex, 3) highest completed household education, 4) immigration status, 5) disposition for mental illness, 6) mental illness and 7) family structure.

As an explorative outcome, a logistic regression model adjusted for change in BMI z-score (from inclusion to follow-up) will be performed to remove the potential effect of weight change on the

association between exposure and psychosocial well-being. The BMI z-score observed closest to the included DNWQ at follow-up will be used.

If possible, we wish to investigate the stratified effect of sex, BMI z-score at inclusion, parental level of education, immigration status, disposition for mental illness and change in BMI z score before we examine their potential for effect modification for the impact in psychosocial well-being for the items Q1-Q4 for the decided not to participate group compared to the non-intervention and intervention groups.

Results:

Figure 1:

Lexi diagram for time of inclusion (x-axis), inclusion age of the participants (y-axis), and time points for the DNWQ.

[figure not shown]

Table 1:

Characteristics at inclusion, divided by groups.

	Decided not to participate group	Intervention group	Non-intervention group
	n	n	n
Age at inclusion, median (IQR)			
Sex (% boys)			
BMI z-score at inclusion mean (SD)			
Highest completed household education, n (%)			
Short			
Medium			
Long			
Family type, n (%)			
Two caretakers			
not-two caretakers			
Immigration status (%)			
Danish			
First or second generation immigrants			
Psychiatric diagnosis, child (% yes)			
Parental mental illness (% yes)			

Table 2:

Descriptive presentation of the distribution of answers to each of the items on psychosocial well-being at inclusion and follow-up, divided by groups.

n (%)	Decided not to participate group		Intervention group		Non-intervention group	
	Inclusion	Follow-up	Inclusion	Follow-up	Inclusion	Follow-up
Question 1: Are you happy with your school?						
Good well-being (yes)						
Poor well-being (no)						
Question 2: Do you feel lonely at school? (0-3 grade) Do you feel lonely? (4-9 grade)						
Good well-being (no)						
Poor well-being (yes)						
Question 3: Is anyone teasing you so that you feel sad? (0-3 grade) Have you been bullied this school year? ? (4-9 grade)						
Good well-being (no)						

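### The multivariable models in Tables 3 and 4 pool two DNWQ forms without adjusting for form, grade or age, which confounds the odds ratios if the groups differ in age or form mix and the poor-well-being rate differs by form or age

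*Combined protocol and SAP*

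**What the plan says.** All references are to the combined protocol and SAP.

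- **Outcome.** Grades 0-3 answer 20 items on a 3-point scale. For the older children, "For children in 4th to 9th grade the DNWQ consist of 40 items assessed on a five-point Likert scale ranging from 1 to 5". The cut-off depends on the form: "Responses 1 and 2 for grades 0-3 and response 1-3 for grades 4-9 will be characterized as poor well-being". Q2 to Q5 and Q7 are also worded differently on the two forms. Q3, for example, asks the younger children about teasing and the older ones about bullying over the school year.
- **Inclusion criteria.** Children are 5 to 10 years old at inclusion and have a follow-up questionnaire 1 to 3 years later.
- **Study variables and Statistical methods.** Both sections list the same seven co-variates. The order of entry is "The co-variates are listed in prioritized order: 1) BMI z-score 2) sex, 3) highest completed household education, 4) immigration status", then disposition for mental illness, mental illness and family structure. The number entered is limited: "The multivariable model will be adjusted for no more than 1 co-variate per 10 observations of the least common outcome". The item's answer at inclusion is also in the models.
- **Stratified analyses.** These cover "the stratified effect of sex, BMI z-score at inclusion, parental level of education, immigration status, disposition for mental illness" and change in BMI z-score.
- **Tables.** Table 1 reports age at inclusion by group, and the tests planned for inclusion characteristics would apply to it. Table 2 puts both wordings of an item in one row. Tables 3 and 4 give one crude and one multivariable odds ratio per item, with no split by form.

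**The concern.** School grade decides which scale, cut-off and, for most items, question a child gets. The age and follow-up limits mean that both forms will occur in the follow-up outcome. The groups are not randomised, and each has its own entry event: declining, first attendance, or the first time obesity is recorded. If one group is older, more of its follow-up answers come from the 5-point form. If poor answers are also more or less common on that form, or change with age, the multivariable odds ratio partly compares two questionnaires. A reader could not separate that from an effect of declining.

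The event-count cap does not explain the omission. Form, grade and age are not on the list at all, so they stay out however many events there are.

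**Working it through.** The plan gives no sample size, prevalence, age by group or form split, so there is no figure of its own to reproduce. The check has two parts: whether any planned step handles form or age, and how large the effect could be under stated assumptions.

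**1. Does any planned step handle it?**
- Listed co-variates: none is form, grade or age. BMI z-score is scaled for age, so it cannot stand in for age.
- Item at inclusion: a child may move from the 0-3 form to the 4-9 form before follow-up, so this term does not identify the follow-up form.
- Table 1: it would show an age difference, but no planned step acts on one.
- Table 2 and the stratified analyses: neither separates the forms or age groups.

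**2. Inputs**
- From the documents: follow-up ages run from about 5 + 1 = 6 to 10 + 3 = 13 years. Poor is 2 of 3 categories on one form and 3 of 5 on the other.
- Assumed form effect: answers spread evenly over the categories would give 66.7% and 60% poor, a form odds ratio of (0.667/0.333) / (0.60/0.40) = 2.0/1.5 = 1.33. A second example, 40% against 25% poor, gives (0.40/0.60) / (0.25/0.75) = 2.0. Neither value is a bound.
- Assumed ages: normal, mean 8 and SD 1.4 years, truncated to 5 to under 11. Follow-up has mean 2 and SD 0.4 years, within 1 to 3. The 4-9 form is used from age 10. The latent correlation between the two answers is 0.3 or 0.6.

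**3. Model.** Follow-up item regressed on group and inclusion item by logistic regression, with a true group odds ratio of 1 and 800,000 simulated children per cell. The seven listed co-variates are not simulated.

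**4. Rough check by hand.** ln(OR) is approximately the difference in the share on the 4-9 form times ln(form OR).
- Shares 57% and 43%: 0.14 × 0.288 = 0.040, so OR 0.96 or 1.04. With form OR 2.0: 0.14 × 0.693 = 0.097, so 0.91 or 1.10.
- Shares 64% and 36%: 0.28 × 0.288 = 0.081, so 0.92 or 1.08. With form OR 2.0: 0.28 × 0.693 = 0.194, so 0.82 or 1.21.

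**5. Simulated odds ratios, inclusion item in the model**

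| Mean age gap (years) | Shares on 4-9 form | Form OR 1.33 | Form OR 2.0 |
|---|---|---|---|
| 0.45 | 57% / 43% | 0.956-0.965 or 1.042-1.045 | 0.908-0.914 or 1.095-1.101 |
| 0.93 | 64% / 36% | 0.913-0.924 or 1.079-1.100 | 0.816-0.831 or 1.209-1.212 |

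The two ranges in each cell are for the two directions of the gap. A separate run at a gap of 0.49 years gave about 0.89 for form OR 2.0, hence the 9-11% quoted for a half-year gap.

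**6. When there is no bias.** With equal form mix the odds ratio stays at 1.00 within simulation error. With equal poor rates on both forms it is 0.99-1.00 even at a 65%/35% mix.

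**7. Effect of adjusting.** Across all cells, including some with an added age trend within form, follow-up form alone returns 0.971-1.012, age alone 0.988-1.015, and both together 0.991-1.012.

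**The case against.** The strongest reply is that nothing in the documents shows the groups to differ. All three share the same age limits, and follow-up is drawn towards two years for everyone. Decliners and attenders come through one screening and invitation route, so their ages may be close and any bias in Table 3 negligible. Table 1 would show an age gap. Figure 1, which is not available here, has inclusion age on one axis and may show part of the pattern. Each added co-variate can also push out a pre-specified confounder when an item is rare.

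Most of this stands as a limit on size. It does not remove the gap, because seeing an imbalance is not adjusting for it, and an adjustment chosen after Table 1 is known would be post hoc.

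A reader might infer more than the documents support:
- *That the adjusted odds ratios are biased, or are biased whenever ages differ.* Bias needs both conditions. Different cut-offs and wording make a difference in poor rates plausible, but no rates are given.
- *That the crude rows are also at fault.* They are unadjusted by design.
- *That form and age must both enter the main model.* Either alone removes nearly all of the illustrated bias, and under the assumed ages the two are highly correlated (0.78-0.79).

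**Conclusion.** The point holds in conditional form. The multivariable models pool two differently scored questionnaires, and no planned step adjusts for form, grade or age. Whether this biases the results depends on two things that the documents leave open: a group difference in age or form mix, and a difference in poor rates by form or age.

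Under the assumed inputs, the shift is small for a half-year gap and a form odds ratio of 1.33 (about 4%). It becomes material for a gap near one year and a form odds ratio of 2.0 (17-18% below 1, or 21% above). These figures show scale only; they do not estimate the bias in this study. Table 4 is more exposed than Table 3, because the non-intervention group enters at a different kind of event. The change should be made because it is cheap, with medium confidence that it will matter.

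**What to change.** - **Statistical methods:** add DNWQ form at follow-up (grades 0-3 or 4-9) to the prioritised co-variate list, high enough that the 1-per-10 cap does not drop it. Form is set by school grade on the questionnaire date, so it is not plausibly a consequence of declining.
- **Sensitivity analysis:** add one, either stratified by follow-up form or with age at inclusion added to the model.
- **Table 1:** report the form split at inclusion and at follow-up by group, beside age.

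**Cost.** No new data are needed, since grade must be known to score the outcome. The full list then needs 8 × 10 = 80 observations of the less common outcome instead of 7 × 10 = 70 (90 instead of 80 if the inclusion item also counts). For rare items the lowest-priority co-variate may therefore drop out. In the simulation, adding form widens the group standard error by about 0-3% with little or no age gap and about 4-6% with a gap near one year.

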Statistical analysis plan

Title:

Does deciding not to participate in a lifestyle intervention affect the long-term change in psychosocial well-being for children with obesity?

Suggested authors:

[name]

[name]

[name]

[name]

[name]

[name]

Purpose:

In this plan for statistical analysis, we provide an overview of the study's context and objectives, as well as general aspects of data management and data analysis. The statistical analysis plan will be attached as a supplementary document upon submission.

Introduction

Childhood obesity is associated with an increased risk of developing non-communicable lifestyle diseases later in life(1-4), while reduced psychological well-being often occurs during childhood. Children living with obesity suffer from lower self-esteem, which have been associated with increased level of sadness and loneliness(5). They also experience higher degree of bullying/teasing(6, 7), have lower quality of life (8, 9) and increasing risk of depression (10) as compared to their peers living without obesity.

Family-centered lifestyle interventions including a multifactorial approach are still considered the first line of treatment when handling childhood obesity(11, 12). The literature suggest that this type of intervention can stabilize or to some extent reduce weight when treating children with obesity(12-14).

Previous studies have reported life stressors, societal norms of weight and body size, as well as earlier experiences with the health care system to be the primary determinants for caregivers not letting their children with obesity participate in lifestyle interventions(15-17).

However, no studies have been able to describe if deciding not to participate in a lifestyle intervention potentially affect the psychosocial well-being in children with obesity.

Objective

To investigate the impact in psychosocial well-being for children with obesity deciding not to participate in a family-centered lifestyle intervention (deciding not to participate group) compared to children who attended the intervention (intervention group), and to children never invited into the intervention (non-intervention group). As a secondary objective, we aim to investigate the effect that is not caused by the weight change by adjusting for this.

Material and methods

Design

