This is an observational cohort study investigating the impact in psychosocial well-being for children with obesity deciding not to participate in a lifestyle intervention. Data will be obtained from mandatory health check-ups at school, Danish national registries, and Danish National Well-being Questionnaire (DNWQ).

Participants

Children were screened by a community health nurse during school time. If the child's BMI (age- and sex-adjusted) was above 30 kg/m^2 , the parents would be informed and invited to participate in the local lifestyle intervention. If the parents accepted, they would be referred to the intervention. The intervention had a maximum duration of one year and typically consisted of 3-4 consultations with a specialized community health care nurse.

This study will include children with obesity with an inclusion visit between August 1st, 2014, and June 30th, 2020, from the city of Aarhus. February 1st, 2023, will be the last day of follow-up (figure 1). The inclusion visit will be defined as the day of deciding not to participate in the intervention (decided not to participate group), the first day of attending the intervention (intervention group), or the first observation with obesity (non-intervention group).

The groups

- Decided not to participate group: Children with obesity declining to participate in a lifestyle intervention.
- Intervention group: Children with obesity who attended the lifestyle intervention.
- Non-intervention group: Children with obesity never invited into the intervention.

Inclusion criteria

1. An inclusion visit between August 1st, 2014, and June 30th, 2020 (figure 1).
2. Obesity at time of referral as defined by the International Obesity Task Force (IOTF) guideline(18).
3. A measure of weight and height within 6 months before or after time of inclusion
4. Age at inclusion between 5 to 10 years of age.
5. A completed DNWQ at inclusion:
 - The deciding not to participate / non-intervention group - with a timeframe between 6 months prior to and 6 months after inclusion.
 - The intervention group - with a timeframe between 10 months prior to and 2 months after inclusion.
6. A completed DNWQ at follow-up (1 to 3 years after inclusion).

Exclusion criteria

1. Children first decided not to participate, but subsequently accepting the intervention.

Outcome

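### A follow-up BMI is not guaranteed for every child, so the weight-adjusted model may rest on different children, or on mistimed values, and is not directly comparable with the full-cohort model

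*Combined protocol and SAP*

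**What the plan says.** The Objective section sets a secondary aim: "we aim to investigate the effect that is not caused by the weight change by adjusting for this". The Statistical methods section serves it with an explorative analysis in which "a logistic regression model adjusted for change in BMI z-score (from inclusion to follow-up) will be performed". For the follow-up value it says only: "The BMI z-score observed closest to the included DNWQ at follow-up will be used".

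Inclusion criterion 3 asks for "A measure of weight and height within 6 months before or after time of inclusion". Criterion 6 asks for "A completed DNWQ at follow-up (1 to 3 years after inclusion", which concerns the questionnaire alone. No criterion asks for a later height and weight.

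On missing data the plan states: "For missing data (education, immigration status, and family-type), a multiple imputation (MI) with chained equations will be utilized". Neither follow-up BMI nor change in BMI z-score is on that list.

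Under Design, "Data will be obtained from mandatory health check-ups at school". Under Data sources, TM-Sund is described as "used to record data on height and weight obtained from health check-ups at the school". The timing and completeness of these check-ups are not given.

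**The concern.** The weight-adjusted model needs two BMI values per child, and the plan secures only the first. It does not state which children the model is fitted in, what happens to a child with no later measurement, or how far from the follow-up questionnaire a measurement may lie.

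An adjusted OR tells a reader little about the role of weight unless it is set against the OR without that adjustment. The only such estimates planned are the multivariable rows of Tables 3 and 4, fitted in the full cohort. If some children leave the weight-adjusted model, the two ORs describe different children. A shift between them could then be read as weight explaining the association, or a lack of shift as weight not explaining it, when the cause is the change of sample.

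**Working it through.** **1. What the text guarantees.** The inclusion measurement lies between 6 months before and 6 months after inclusion. The follow-up questionnaire lies 12 to 36 months after inclusion. The inclusion measurement can therefore be as close as 12 − 6 = 6 months to the follow-up questionnaire, or as far as 36 + 6 = 42 months. The rule to take the closest value has no maximum distance and does not require a value later than the inclusion measurement. A child with no later measurement can be handled in two ways:

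- There is no follow-up value, and ordinary logistic regression drops the child.
- Read literally, the closest value is the inclusion value, so change = 0. The child stays in, but weight change is not adjusted for in that child. This cannot be sized from the documents.

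The remaining steps concern the first reading. The documents give no sample size, event count or missing rate, so there is no figure of the plan's to reproduce, and **every input below is an assumption**.

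**2. Noise from the change of sample.** Assume n children per group, a proportion p = 0.30 with poor well-being in both groups, a fraction m of follow-up BMI missing completely at random, and no mediation.

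- Full cohort: Var(log OR) = 2 / [n p (1 − p)]. With n = 100: 2 / (100 × 0.30 × 0.70) = 0.0952, SE 0.309.
- Subset: divide by (1 − m). With m = 0.30: 0.0952 / 0.70 = 0.1361, SE 0.369.
- The subset is nested in the cohort, so the variance of the difference is the subset variance minus the full variance: 0.1361 − 0.0952 = 0.0408, SD 0.202.
- 95% range of the OR ratio: exp(±1.96 × 0.202) = 0.67 to 1.49.

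| n per group | Missing | 95% range of subset OR / full-cohort OR |
|---|---|---|
| 100 | 10% | 0.82–1.22 |
| 100 | 30% | 0.67–1.49 |
| 100 | 50% | 0.55–1.83 |
| 200 | 30% | 0.76–1.32 |

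A simulation (600 runs, 300 children in two groups, adjusted for well-being at inclusion, no weight effect) compared the weight-adjusted OR in the subset with the main OR in the full cohort. The range was 0.69–1.42 at 30% missing and 0.59–1.77 at 50%. With both models fitted in the same children it was 0.89–1.14 and 0.87–1.18.

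**3. When there is bias.** Let s be the probability of having a follow-up BMI, indexed by group (1 = declined) and outcome (1 = poor). Selection multiplies the OR by (s11 × s00) / (s10 × s01).

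- Availability depending on group only (70% against 90%): (0.70 × 0.90) / (0.70 × 0.90) = 1.00.
- Availability depending on outcome only (70% poor, 80% good, in both groups): (0.70 × 0.80) / (0.80 × 0.70) = 1.00.
- Joint dependence, 65% (poor) and 80% (good) among decliners, 90% in the comparator: (0.65 × 0.90) / (0.80 × 0.90) = 0.81.
- Stronger joint dependence, 50% and 80% against 90%: (0.50 × 0.90) / (0.80 × 0.90) = 0.63.

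**4. What a same-children comparison repairs.** Simulated with 1,000,000 children and the 65%/80% against 90% pattern:

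| Assumed weight effect | Full cohort, no weight change | Subset, no weight change | Subset, weight-adjusted |
|---|---|---|---|
| None | 1.49 | 1.21 | 1.21 |
| Log-OR 0.5 per z-unit | 1.63 | 1.33 | 1.21 |

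With no weight effect, 1.49 against 1.21 is a false difference, and it vanishes within the subset. With a real weight effect and complete data, the OR moves from 1.63 to 1.49, a ratio of 1.63 / 1.49 = 1.09. The cross-sample comparison gives 1.63 / 1.21 = 1.35; the same-children comparison gives 1.33 / 1.21 = 1.10, close to the truth. Both subset ORs still sit below their full-cohort counterparts, so the refit does not remove selection itself.

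**The case against.** The strongest reply is that no child need be missing. The check-ups are called mandatory, and the documents report no missing count. A reader might infer that change in BMI z-score cannot be derived for some children and that the model certainly runs on a subset. The documents do not support that; they support only that a value is not guaranteed. The reply does not settle the matter, however. The plan makes a height and weight near inclusion an entry condition, which would be redundant if check-ups always supplied one in time.

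Second, the plan never says it will set the two models side by side or interpret the movement of the OR. Its stated target is the adjusted association, and Tables 3 and 4 have no row for the weight-adjusted model. This stands: the problem lies in a comparison that readers are likely to make, not in one the plan promises.

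Third, a reader might infer bias because intervention children attend nurse consultations, typically 3–4, and so may be measured more often. Availability that differs by group alone leaves the OR unbiased (step 3). The intervention also lasts at most one year, while follow-up is at 1 to 3 years. Nothing in the documents shows the joint dependence on group and outcome that bias requires.

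Fourth, the model is labelled explorative. That limits the consequence, although the Objective section calls the same question secondary.

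**Conclusion.** The point holds in a limited form. The plan does not secure a follow-up BMI, does not impute it, does not define it in time, and does not state the children in whom the weight-adjusted model is fitted. If any are dropped, that model's OR is not directly comparable with the full-cohort multivariable OR. If they are kept with a mistimed value, the adjustment is incomplete for them.

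Under the dropping reading, the plain consequence is noise: a 95% range of about 0.67 to 1.49 for the ratio of the two ORs with 100 per group, 30% poor well-being, 30% missing completely at random and no mediation. The range narrows with fewer missing or more children, and disappears if every child has a properly timed later BMI. Bias is possible but conditional on joint dependence, for which the documents give no evidence either way. It would be wrong to conclude that any difference between the two models is an artefact, or that the main results are at risk: the comparisons in Tables 3 and 4 do not use follow-up BMI.

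**What to change.** Add to the paragraph on the explorative model in Statistical methods:

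- *The follow-up BMI z-score must post-date the inclusion measurement and lie within a prespecified window of the follow-up DNWQ. The number and percentage of children with such a value will be reported by group.*
- *For each item and each contrast, the multivariable model without change in BMI z-score will be refitted in exactly the children with a follow-up BMI, with the same other covariates, and reported beside the weight-adjusted model with n per group.*
- *Any statement on the contribution of weight change will be based on these two models. The full-cohort estimate will be shown alongside so that selection into the subset is visible.*

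The same-covariates condition matters because the limit of one covariate per 10 observations of the rarer outcome could otherwise admit fewer covariates in the smaller sample. The full-cohort estimate must stay in view because the refit removes the false between-model difference but not selection (step 4).

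The cost is one extra model fit per item and contrast, 7 × 2 = 14 fits, and a few sentences. No new data are needed. The authors must choose the window; a narrower one gives better-timed values but may leave fewer children.
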